#### 6.4.5 Intraoperative Data Collection

The following data will be recorded on the Intraoperative CRF:

- Surgical procedure(s)
- Description of TBS
  - Location
  - Conventional means for hemostasis (pressure, suture, cautery, etc.)
- Confirmation of intraoperative eligibility criteria
- Approximate dimensions of target bleeding site
- SPOT GRADETM scores at baseline
  - Assessment of intraoperative eligibility
  - o Immediately prior to hemostatic device application
- SPOT GRADE™ score at 3 minutes
- SPOT GRADETM score at 5 minutes (if hemostasis is not achieved within 3 minutes)
- Randomization
  - Time of randomization
  - o Treatment arm
  - Device lot/batch number data
- Number of incidence(s) of interruption of hemostatic device preparation

- Satisfaction on time and ease of hemostatic device preparation
- Incidence of TBS re-bleeding prior to subject closure
- Incidence of any device deficiencies
- Incidence of any device-related adverse events

Table 7 below shows a timeline of intraoperative procedures.

Time Point (MM:SS)	Study Procedures or Assessments
Prior to 00:00	• Identify Target Bleeding Site (TBS)
	
 
Assign SPOT GRADE™ score
 

	Perform randomization
00:00 (start stopwatch)	
 
Open HEMOBLAST™ or FLOSEAL
 

	packaging and start preparation
0X:XX	• Assign SPOT GRADE ™ score immediately
	prior to hemostat application
03:00	
 
Assign SPOT GRADE™ score
 

	If SPOT GRADE TM score = $0$
	Intraoperative efficacy evaluation completed
	If SPOT GRADE TM score is NOT $0$
	
 
Re-apply HEMOBLASTTM or FLOSEAL
 

05:00	
 
Assign SPOT GRADE™ score
 

	If SPOT GRADE TM score = $0$
	Intraoperative efficacy evaluation completed
	If SPOT GRADE™ score is NOT 0
	Rescue treatment

#### Table 7. Timeline for Intraoperative Procedures\*

\* Assuming subject meets all intraoperative eligibility criteria

#### 6.5 Discontinuation Procedures and Documentation

Subjects will be discontinued after completion of the intraoperative visit.

The Discontinuation CRF should be completed to document the reason for discontinuation:

- Subject has completed the study;
- Subject withdrawal and reason for withdrawal; or
- Subject death (prior to completion of study evaluations).

The date of discontinuation will also be noted on the Discontinuation CRF.

## 7 ADVERSE EVENTS

## 7.1 General

An adverse event (AE) is 'any untoward medical occurrence in a subject'.

A device deficiency is defined as the inadequacy of a medical device with respect to its identity, quality, durability, reliability, safety or performance, which may include device malfunctions, use errors and inadequate labeling.

Only Adverse Events (AEs) possibly, probably, or definitely related to the hemostatic device (using the definitions below) will be recorded as part of this clinical study. Anticipated adverse device effects are included in Section 12.

## 7.2 Adverse Event Documentation

Only Adverse Events (AEs) possibly, probably, or definitely related to the hemostatic device (using the definitions below) will be recorded as part of this clinical study. AEs not related to the hemostatic device (the AE is due to the underlying disease state or is due to concomitant medications or therapy not related to the use of the hemostatic device) will not be recorded as part of this clinical study.

AEs will be documented by the Investigator on the appropriate source document(s) at the study site and also on the Adverse Event CRF. Adverse events are to be recorded and dated according to when they are first observed. The subsequent treatment(s) should also be documented. The following will be recorded on the Adverse Event CRF:

- Accepted medical term for the AE;
- Description of the event;
- Date of onset;
- Date of resolution, if applicable;
- Outcome;
- Treatment(s)/action(s) taken;
- Severity;
- Relationship to the hemostatic device; and
- Determination of reportability (see Reporting Section below).

The severity of the event will be determined by the Investigator using the following definitions:

- Mild: the symptoms are transient, barely perceptible by the subject and do not hinder normal activity; no treatment is usually prescribed to reduce these symptoms;
- Moderate: the symptoms are sufficiently severe to provoke discomfort in the subject and sufficiently uncomfortable to prevent normal activity; a treatment may be required; or
- Severe: the symptoms considerably modify the normal course of the subject's activities or are disabling or are life-threatening; the treatment studied should be suspended; a treatment for the symptoms is prescribed.

The relationship to the hemostatic device will be determined by the Investigator using the following definitions:

- Possibly related: the AE has a reasonable temporal relationship to the use of the hemostatic device but alternative etiology is equally or more likely compared to the potential relationship to the use of the hemostatic device;
- Probably related: the AE has a strong temporal relationship to the use of the hemostatic device and alternative etiology is less likely compared to the potential relationship to the use of the hemostatic device; or

• Definitely related: the AE has a strong temporal relationship to the use of the hemostatic device, follows a known response pattern and cannot reasonably be explained by known characteristics of the subject's clinical state or other therapies.

The expectedness of the AE will be determined by the Investigator as:

- Anticipated; or
- Unanticipated.

Anticipated AEs are those that are identified as potential risks in the device labeling (e.g., IFU). Unanticipated AEs are those that are, by their nature, incidence, severity, or outcome, not identified in the device labeling.

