## 6.4 Intraoperative Procedures and Evaluations

All subjects will undergo the same intraoperative study evaluations. Intraoperative is defined as the time interval from when the subject enters the surgical suite until the subject exits the surgical suite.

Subjects undergoing the non-emergent cardiothoracic surgeries are eligible for enrollment into the clinical study. The Investigator will perform the surgery per his or her standard procedures, including conventional methods of hemostasis where practical (pressure, ligature, cautery, etc.).

Both test and control devices (not opened or prepared) should be available at the start of each procedure.

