11.3.2.2 Methods of Analysis

Summaries of the number and percent of subjects with at least one device-related AE will be provided. Comparisons of the proportion of subjects experiencing SADEs and UADEs will be made between treatment arms.

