FDA	Food and Drug Administration
ICF	Informed Consent Form
Intraoperative Time	Time from skin open to skin closure
IRB	Institutional Review Board
QA	Quality Assurance
SADE	Serious Adverse Device Effect – an adverse device effect that has
	resulted in any of the consequences characteristic of a serious
	adverse event or that might have led to any of these consequences if
	suitable action had not been taken or intervention had not been
	made or it circumstances had been less opportune
SAE	Serious Adverse Event – an adverse event that:
	• Led to death

	Led to a serious deterioration in the health of the subject, that either resulted in a life-threatening illness or injury, or a permanent impairment of a body structure or a body function, or in-patient hospitalization or prolongation of existing hospitalization, or resulted in medical or surgical intervention to prevent life-threatening illness or injury or permanent impairment to a body structure or a body
	function.
SBSS	Surface Bleeding Severity Scale, also known as SPOT GRADE™
TBS	Target Bleeding Site
TTH	Time To Hemostasis
UADE (also USADE)	Unanticipated [Serious] Adverse Device Effect – any serious adverse effect on health or safety, any life-threatening problem or death caused by, or associated with a device, if that effect, problem, or death was not previously identified in nature, severity, or degree of incidence in the application; or any other unanticipated serious problem associated with a device that relates to the rights, safety or welfare of subjects
WHO	World Health Organization

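### Adverse events enter the study data only if an investigator who knows the arm calls them device-related, and no all-cause count of serious events exists to check that attribution

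*Combined protocol and SAP*

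**What the plan says.** Section 7.2 states the recording rule: "Only Adverse Events (AEs) possibly, probably, or definitely related to the hemostatic device (using the definitions below) will be recorded". Section 7.1 states the same rule, so it is deliberate. Section 7.2 adds that events not related to the device "will not be recorded as part of this clinical study". On who decides, it says: "The relationship to the hemostatic device will be determined by the Investigator using the following definitions".

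The lowest recorded category, possibly related, asks for a reasonable temporal relationship and admits events for which another cause is as likely or likelier. Unrelated events are those due to the underlying disease or to other therapy.

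Section 7.3 defines an SAE, but its 24-hour reporting duty covers only SADEs and UADEs. Section 11.1.3 summarises device malfunctions, device-related AEs, SADEs and UADEs by treatment group. Section 11.3.2.2 goes further: "Comparisons of the proportion of subjects experiencing SADEs and UADEs will be made between treatment arms". It names no test or significance level. No section plans a table of SAEs regardless of cause.

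**The concern.** Relatedness is normally a field on an adverse event form. Here it also decides whether the form exists. The person deciding has just used the device, and the boundary is loose: an intraoperative event with a likelier surgical cause can fit either the possibly related or the unrelated description. Section 6.4.4 loosens it further, since either hemostat may be used at other bleeding sites and no study data are collected there.

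If investigators are readier to attribute events to one product than to the other, the by-arm safety tables will show a difference that is not in the patients, or hide one that is. With no all-cause count, a reader of the final report could not tell a difference in events from a difference in attribution.

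**Working it through.** **Step 1: does the person deciding relatedness know the arm?** The documents never use the terms blinded or open-label, so this is inferred. Section 6.4.2 has the assigned hemostat opened, prepared and applied after randomization. Section 8.4 says that investigators apply the devices. Section 3.1 describes a dry powder that needs no preparation; Section 3.3 describes a preparation kit. No section describes a masked assessor or an adjudication committee. The inference is safe.

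**Step 2: what is captured without a relatedness condition?**

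| Item | Where | Relatedness required? |
|---|---|---|
| Adverse events, serious or not | 7.1, 7.2 | Yes |
| Death before completion of study evaluations | 6.5 (Discontinuation CRF), 9.1 | No |
| Device deficiencies | Table 3, 6.4.5 | No |
| Re-bleeding at the target site before closure | 6.4.3, 6.4.5 | No |

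A non-fatal SAE judged unrelated has no adverse event record and reaches no safety table.

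**Step 3: the plan's own figures.** No figure is given for safety. The only calculated design figure is the efficacy sample size in 11.3.3. It reproduces: 0.40 v 0.10, one-sided 0.025, 90% power and a continuity correction give 49 per arm. Then 98/0.95 = 103.2, so 104 in total and 52 per arm, the number used below.

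**Step 4: what differential attribution could do.** The event rates and attribution probabilities are assumptions, because the documents give none.

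Expected recorded events per arm = 52 × true rate × probability of attribution to the device.

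With equal true rates in both arms, the ratio of recorded rates is the ratio of attribution probabilities, whatever the true rate. The last two columns give the chance of a nominally significant difference (two-sided 0.05, exact binomial enumeration). Both tests are shown because the plan names none.

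| True rate, both arms | Attribution, arm A v arm B | Expected recorded events | Ratio | Fisher | Wald |
|---|---|---|---|---|---|
| 10% | 50% v 50% | 2.6 v 2.6 | 1.0 | 1% | 6% |
| 10% | 25% v 50% | 1.3 v 2.6 | 0.5 | 1% | 9% |
| 10% | 20% v 80% | 1.0 v 4.2 | 0.25 | 10% | 31% |
| 20% | 25% v 50% | 2.6 v 5.2 | 0.5 | 7% | 18% |
| 20% | 20% v 80% | 2.1 v 8.3 | 0.25 | 39% | 59% |
| 40% | 25% v 50% | 5.2 v 10.4 | 0.5 | 21% | 32% |
| 40% | 20% v 80% | 4.2 v 16.6 | 0.25 | 84% | 90% |

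Example, second row: 52 × 0.10 × 0.25 = 1.3 and 52 × 0.10 × 0.50 = 2.6.

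**Step 5: masking.** Suppose true rates of 40% v 20% and attribution of 25% v 50%. Recorded rates are 0.40 × 0.25 = 10% and 0.20 × 0.50 = 10%. A twofold difference disappears. With all events recorded, it would reach nominal significance 52% of the time by Fisher and 63% by Wald.

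**Step 6: reading these results.** At low rates the harm is a distorted ratio on very few events, seldom a falsely significant test. Large effects need both frequent events and strongly unequal attribution.

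**The case against.** The strongest objection is that SADEs and UADEs are device-attributed by definition (7.3, Section 16). Comparing them involves judgement under any recording rule, and recording more events does not change that. This stands. A reader might infer that the filter alone spoils the comparison, or that wider recording would make it objective. The documents support neither: what is missing is an all-cause count to compare it with.

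Second, the possibly related category is broad, and an investigator who applied it literally would record most events that follow application. This softens the filter. It does not standardise it, because the unrelated description overlaps with it.

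Third, a reader might infer that an SAE called unrelated leaves no trace. That goes too far. Deaths before completion of evaluations go on the Discontinuation CRF (6.5), subjects agree to review of their hospital records (14.2), and monitors may inspect those records (15.3). Hospital records are not, however, the source of any planned safety table.

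Fourth, a reader might infer that the adverse event window is defined two ways. Section 6.4 defines intraoperative as "the time interval from when the subject enters the surgical suite until the subject exits the surgical suite", and Section 16 defines intraoperative time as "Time from skin open to skin closure". But no adverse event section names either as its collection window, so this is a difference in terminology and not a contradiction in safety capture.

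Fifth, the study is post-market, uses the test device within its approved indication (12.3), has no follow-up visits (5.8), and leaves safety out of study success (11.1.4). Restricting capture to device-related events is an open and consistent choice. That limits the weight of the point, but the plan still compares arms on the filtered events.

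**Conclusion.** The concern holds in a limited form. All adverse event data by arm, and the SADE and UADE comparison, pass through one judgement by an investigator who knows the arm. Apart from early deaths, the study data contain no all-cause serious-event count against which to check it.

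The direction and size of any bias cannot be estimated from the documents. The illustrations show a recorded ratio of 0.5 or 0.25 when true rates are equal, and a twofold true difference erased, but only under assumed attribution probabilities. They use rates for events in general; serious events may well be rarer, which puts the lower rows of the table out of reach. The verdict also rests on the inference that no masking is intended.

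The primary endpoint, the sample size and the definition of study success are untouched. The change is worth making because it is cheap; the plan is not invalid without it.

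**What to change.** - In 7.1 and 7.2, require every SAE and every death from hemostat application to exit from the surgical suite to be recorded regardless of relatedness. Keep relatedness as a field on the existing Adverse Event CRF, with an added unrelated category.
- Leave non-serious recording limited to device-related events.
- In 11.1.3 and 11.3.2.2, tabulate all-cause SAEs by arm beside SADEs and UADEs.

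Setting the period out in 7.1 and 7.2 also avoids relying on either definition of intraoperative.

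The cost is a few extra forms, completed by staff already present, with no added visit. Some background surgical events will appear in the table; randomization makes them comparable between arms in expectation. The gain is a between-arm count of serious events that does not depend on attribution. The SADE and UADE counts, and the non-serious summary, will still depend on it.

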## 7.3 Reporting

A serious adverse event (SAE) is defined as an adverse event that:

- Led to death;
- Led to a serious deterioration in the health of the subject, that either resulted in a life-threatening illness or injury, or a permanent impairment of a body structure or a body function, or in-patient hospitalization or prolongation of existing hospitalization, or resulted in medical or surgical intervention to prevent life-threatening illness or injury or permanent impairment to a body structure or a body function; or
- Led to fetal distress, fetal death, or a congenital abnormality or birth defect.

A serious adverse device effect (SADE) is defined as an adverse device effect that has resulted in any of the consequences characteristic of a serious adverse event or that might have led to any of these consequences if suitable action had not been taken or intervention had not been made or if circumstances had been less opportune.

An unanticipated [serious] adverse device effect (UADE/USADE) is any serious adverse effect on health or safety, any life-threatening problem or death caused by, or associated with a device, if that effect, problem, or death was not previously identified in nature, severity, or degree of incidence in the protocol; or any other unanticipated serious problem associated with a device that relates to the rights, safety, or welfare of subjects.

All SADEs and UADEs must be reported to the Sponsor representative within 24 hours of the Investigator becoming aware of it.

There are two methods of reporting. The first is to complete and save the Adverse Event CRF within 24 hours of the Investigator becoming aware of the SADE or UADE.

The second method of reporting is to contact the Sponsor representative for event reporting:

[contact] E-Mail: [contact]

The Investigator should institute appropriate therapeutic and follow-up measures in accordance with good medical practice and record them in the subject's source documentation and on the Adverse Event CRF. It

is the responsibility of the Principal Investigator to inform the appropriate personnel as required by IRB policy.

For SADEs and UADEs that are unresolved at the time of subject discontinuation, the Investigator will continue to follow the event to resolution or stabilization per standard medical care.

## 7.4 **Regulatory Authority Reporting**

The study site will provide Sponsor-requested [redacted] details regarding the SADE or UADE and the Sponsor Regulatory Affairs Department will be notified to determine reportability per applicable regulations and guidelines. Sponsor reporting to FDA will be performed per 21 CFR Part 803.

## 8 DATA COLLECTION

## 8.1 Completion of Case Report Forms

Prior to enrollment of subjects at each study site, the Sponsor representative will provide the Principal Investigator and designated study site staff with training on electronic CRF completion procedures. The Principal Investigator will be responsible for the timing, accuracy, and completeness of CRFs for each individual subject. The personal data recorded on all paper and electronic documents will be regarded as confidential.

## 8.2 Source Documentation

Source documents are where clinical study information for subjects are first recorded. Data collected for the clinical study must be supported by source documents, and may include, but is not limited to, subject medical records, hospital charts, operative reports, laboratory and diagnostic test reports, and study worksheets. Study worksheets should be used when other source documents do not capture study-specific data as part of standard of care.

## 8.3 Retention of Clinical Study Documentation

Clinical study records will be stored in a confidential manner so as to protect the confidentiality of subject information. All records related to this clinical study will be retained in appropriate study files.

The Principal Investigator is responsible for retaining all copies of the records for a period of no less than 5 years from the date on which the clinical study is completed/terminated. In all cases, the Principal Investigator must contact the Sponsor prior to disposing of any records related to the clinical study.

The Sponsor must approve the destruction of any study records.

In addition, if the Principal Investigator moves/retires, etc., he/she should provide the Sponsor with the name and address of the person who will look after and be responsible for the clinical study related records.

## 8.4 Training

Principal Investigators and study site staff will be trained on the clinical study and the specific tasks to which they are delegated. Study site staff will also have documented training on Good Clinical Practice.

Further, Investigators (Principal Investigators and sub-investigators responsible for enrolling study subjects and applying the hemostatic devices) will have training on use of the test device, control device, and the SPOT GRADETM.

# 9 TERMINATION OF THE CLINICAL STUDY

## 9.1 Subject Withdrawals and Discontinuation

During the course of this clinical study, subjects may elect to withdraw from study participation for any reason. In addition, subjects will be withdrawn from the study for any of the following reasons:

- TBS bleeding severity not appropriate for treatment immediately prior to hemostat application, but after enrollment and randomization; or
- Subject death (prior to completion of study evaluations).

Subjects who are withdrawn prior to receiving test or control device will be replaced.

#### 9.2 Early Termination of the Clinical Study

Both the Sponsor and Principal Investigator reserve the right to terminate the clinical study at any time. Should this be necessary, the procedures will be arranged on an individual site basis after review and consultation by both parties. In terminating the clinical study, the Sponsor and the Principal Investigator will assure that adequate consideration is given to the protection of the subjects' interests. In case the study is terminated for safety reasons, this will be communicated to all participating Principal Investigators, who will be responsible for notifying their reviewing IRBs per IRB policy.

#### **10 DATA MANAGEMENT**

All data will be housed in a validated database program.

Once all the subject data has been collected, the analysis and reporting will be conducted. Any data existing for subjects who have not received treatment will not be used in the analysis.

Any data existing for subjects who have received the test or control device, who withdraw voluntarily or who are withdrawn from the clinical study, will be used in the final analysis. The inclusion of partial data will be documented in the final report. The final report will be the responsibility of Biom'up.

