## 5.7 Withdrawal Criteria

Subjects may withdraw from the study at any time without providing a reason. Subjects will not be penalized nor lose any benefits to which they are otherwise entitled if they should choose to withdraw. The Investigator may also choose to withdraw the subject if he or she feels that this is in the subject's best interest.

Subjects who withdraw from the study before receiving the test or control hemostatic device will receive routine care. No study-specific assessments will be conducted.

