## 11.1.3 Safety Outcomes

The rate of occurrence of device malfunctions, device-related AEs, SADEs, and UADEs will be summarized for each treatment group. Events will be summarized by severity.

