## **11.2.1** Analysis Populations

Safety analyses will be performed on the Full Analysis Population, defined as all subjects who were randomized into the study and received study intervention. Efficacy analyses will be conducted on the time to hemostasis (TTH) Analysis Population, defined as all subjects who were randomized, received study intervention, and had a TTH assessment recorded regardless of whether the measurement was censored (defined as the use of an additional hemostatic product or surgical rescue prior to the end of observation time, or failing to achieve and maintain complete hemostasis prior to the end of observation time). Data summaries will be based on the intervention received, regardless of which intervention was randomly assigned.

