## 11.3.2 Analysis of Safety Outcomes

11.3.2.1 Analysis Population

Safety analyses will be conducted on the Safety Analysis Population, defined as all subjects who were randomized into the study and received study intervention.

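### The by-arm device-malfunction rate leaves out malfunctions in randomized subjects whose assigned package was opened but who received no study device

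*Combined protocol and SAP*

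**What the plan says.** Section 11.1.3 sets the outcome: "The rate of occurrence of device malfunctions, device-related AEs, SADEs, and UADEs will be summarized for each treatment group".

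The population is defined twice, under two names but with the same content. Section 11.2.1: "Safety analyses will be performed on the Full Analysis Population, defined as all subjects who were randomized into the study and received study intervention". Section 11.3.2.1: "Safety analyses will be conducted on the Safety Analysis Population, defined as all subjects who were randomized into the study and received study intervention".

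Section 10 then applies a general exclusion, with no exception for device deficiencies: "Any data existing for subjects who have not received treatment will not be used in the analysis". Section 9.1 adds: "Subjects who are withdrawn prior to receiving test or control device will be replaced". For subjects who withdraw before receiving a device, section 5.7 says: "No study-specific assessments will be conducted".

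Section 7.1 does not make a deficiency depend on the device reaching the patient: "A device deficiency is defined as the inadequacy of a medical device with respect to its identity, quality, durability, reliability, safety or performance". It goes on to include malfunctions, use errors and inadequate labeling. Table 3 provides a Device Deficiency CRF, to be completed as applicable. Section 6.4.5 lists device deficiencies and lot or batch number among the intraoperative data.

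**The concern.** A malfunction rate should count every occasion on which a device was opened for use and failed. Here the denominator is restricted to subjects in whom a device was applied, and a malfunction can be one reason why it was not. An event of that kind may be recorded on the Device Deficiency CRF and still be barred from the analysis, after which the subject is replaced by one who was treated.

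What is at stake is how the reported figure can be read. A result of 0% in an arm could mean that no device malfunctioned, or that the malfunctions occurred in subjects who were left out. The final report as planned would not let a reader tell which.

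A smaller gap lies beside this one. The CRFs collect all deficiencies, but section 11.1.3 names only malfunctions, so use errors and labeling problems have no planned summary.

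**Working it through.** **1. The plan's own figures.** The documents state no expected malfunction rate, so there is none to reproduce. The only planned number used here is 52 per arm, which does reproduce.
- Inputs (11.3.3): 0.40 versus 0.10, one-sided alpha 0.025, power 0.90. The mean proportion is 0.25.
- Uncorrected pooled formula: n = [1.960 × √(2 × 0.25 × 0.75) + 1.282 × √(0.40 × 0.60 + 0.10 × 0.90)]² / 0.30² = 41.7, so 42.
- With continuity correction: (41.7/4) × [1 + √(1 + 4/(41.7 × 0.30))]² = 48.1, so 49 per arm and N = 98, as stated.
- With 5% attrition: 49/0.95 = 51.6, so 52 per arm and N = 104, as stated.

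Nothing in this point alters these figures.

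**2. Can a subject have the package opened and end untreated?** Yes, on the protocol's own sequence.
- Section 6.4.2: randomization comes first, then the assigned hemostat is opened (stopwatch 00:00), prepared and applied.
- Section 6.4.1 and Table 7: bleeding is graded again just before application, which is after opening. If the grade is no longer minimal, mild or moderate, that site is not treated. If no other suitable site is found, the subject is withdrawn.
- Section 9.1 lists this as a withdrawal reason and replaces the subject.

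A deficiency found during opening or preparation in such a subject meets the section 7.1 definition. It is then removed by section 10 and by both population definitions.

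**3. Does anything restore it?** No. Sections 7.3 and 7.4 concern expedited and regulatory reporting and do not enter the by-arm rate. No section provides an opened-package denominator or a separate listing for untreated subjects.

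**4. Effect on the rate.** Let k be malfunctions among the 52 treated in an arm, and m be subjects whose device malfunctioned after opening and who ended untreated and were replaced.
- Planned rate: k/52.
- Rate with those subjects restored: (k + m)/(52 + m).
- Difference: m(52 − k)/[52(52 + m)], which is never negative.

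All counts below are assumptions.

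| k | Planned | m = 1 | m = 2 | m = 3 | m = 5 |
|---|---|---|---|---|---|
| 0 | 0/52 = 0.0% | 1/53 = 1.9% | 2/54 = 3.7% | 3/55 = 5.5% | 5/57 = 8.8% |
| 1 | 1/52 = 1.9% | 2/53 = 3.8% | 3/54 = 5.6% | 4/55 = 7.3% | 6/57 = 10.5% |
| 2 | 2/52 = 3.8% | 3/53 = 5.7% | 4/54 = 7.4% | 5/55 = 9.1% | 7/57 = 12.3% |

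**5. A refinement.** A full opened-package denominator also brings in u untreated subjects with no malfunction, giving (k + m)/(52 + m + u). This exceeds k/52 whenever 52m > k(m + u), and always when k = 0 and m ≥ 1. The count of malfunctions can only rise. The rate could fall slightly only if malfunctions were rarer among the untreated than among the treated.

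**The case against.** The strongest reply is that a treated-subjects population is conventional for safety, that the malfunction rate is descriptive with no role in study success (11.1.4), and that the counts above are invented. The exact two-sided 95% upper limit for 0/52 is 1 − 0.025^(1/52) = 6.8%, which already covers the illustrative 3.7%. These facts stand and limit the importance of the point. They do not answer it: the interval allows for chance, whereas the rule discards events that were observed.

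Three stronger readings are tempting. The documents do not support them.

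- **A reader might infer that a failed kit means the subject is dropped.** Device failure is not among the withdrawal reasons in section 9.1. Section 6.4.2 directs use of the assigned hemostat, and nothing bars a second unit of it. A subject treated with a second unit has received the intervention, and the malfunction can be counted.
- **A reader might infer that the loss falls mainly on FLOSEAL**, because section 3.1 says HEMOBLAST needs no preparation and section 3.3 supplies FLOSEAL as a prep kit. No failure modes or rates are given for either device. A HEMOBLAST unit that failed to dispense could also leave an untreated subject. Neither the direction nor the size of a difference can be derived.
- **A reader might infer that a malfunction would be booked under the other device**, since section 11.2.1 says: "Data summaries will be based on the intervention received, regardless of which intervention was randomly assigned". That requires the other device to be used at the target site after the assigned one fails, which no section describes. Section 6.4 asks for both devices to be available, but allocation happens during surgery, which explains this. Section 6.4.4 allows either hemostat only at other bleeding sites.

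It is also fair to object that the data may not exist for these subjects, given the section 5.7 wording and the absence of a package-opening field in section 6.4.5. This stands, and the remedy has to cover it.

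**Conclusion.** The concern holds in a limited form. By a stated rule, the planned rate omits any malfunction in a randomized subject whose assigned package was opened but in whom no study device was applied. Omitting such events can only understate the rate, by anything from nothing to the whole of it. The true amount depends on how often this happens, which the documents do not say.

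The conclusion assumes that receiving the intervention, which the plan does not define, means having a study device applied. The illustration further assumes 52 treated subjects per arm after replacement, one package counted per subject, and the chosen values of k and m.

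This is worth correcting because the change is cheap and removes an ambiguity from a planned safety result. It is not a threat to the trial's main conclusion.

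**What to change.** - **Section 10:** exempt device deficiencies from the exclusion of untreated subjects.
- **Section 11.1.3:** report device deficiencies by type (malfunction, use error, labeling), not malfunctions alone.
- **Sections 11.2.1 and 11.3.2.1:** for this outcome, use as denominator all randomized subjects whose assigned package was opened, including untreated and replaced subjects. Attribute each deficiency to the device that was deficient, using the recorded lot number. Keep the treated population for the other safety outcomes.
- **Sections 5.7 and 6.4.5:** state that package opening and any device deficiency are recorded for subjects who leave before application, despite the general wording on assessments in 5.7.

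The Device Deficiency CRF and lot data already exist. The cost is the wording changes, one added CRF item for package opening, and possibly a slightly higher reported rate.
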